Statistical Analysis Plan

Protocol Title:	High-Resolution Assessment of Coronary Plaques in a Global Evolocumab Randomized Study (HUYGENS)						
Short Protocol Title:	Imaging of Coronary Plaques in Subjects Treated With Evolocumab						
Protocol Number:	20160184						
NCT Number:	Unavailable for first version						
Authors:	[REDACTED]						
Sponsor:	Amgen Inc. [name]						
SAP Date:	

Document Version	Date	

Original (v1.0)	28 March 2019	

Amendment 1 (v2.0)	15 January 2021	

	Document Version	Date	Original (v1.0)	28 March 2019	Amendment 1 (v2.0)	15 January 2021
Document Version	Date						
Original (v1.0)	28 March 2019						
Amendment 1 (v2.0)	15 January 2021						

Version Number	Date (DDMMYYYY)	Summary of Changes, including rationale for changes
Original (v1.0)	28MAR2019	N/A
Amendment 1 (v2.0)	15 January 2021	
 • Editorial changes were made throughout the document to improve the overall clarity. • Updated section 1 to reflect the planned analysis. • Updated section 5.1.1 regarding the definition of Maximum Lipid Arc and Lipid Core Length, and added definition for Lipid Rich Plaque as per clinical team discussion. • Updated section 5.1.2 regarding the definition of Number of Microchannels and Macrophage Composition, and added definition for Lipid Content as per clinical team discussion. • Updated section 5.3 to differentiate the baseline for Lipid and Lipid-related Parameters, Concomitant Medication Usage and Medical History, and other Baseline Values to reflect true baseline for the endpoints. • Updated section 6.2 to reflect FCT instead of OCT for clarification. • Updated section 6.3 to change “Completer” to “Completers”. • Updated section 6.4 to delete Per-Protocol Analysis Set (PPAS) as per stats team discussion. • Updated section 8.3 to clarify imputation method for secondary endpoints. • Updated section 9.2 and section 9.3 to include COVID-19 Impact related descriptive analysis to measure COVID impact. • Updated section 9.5 to add COVID-19 impact analysis into Sensitivity Analysis for Primary Endpoint for mitigating COVID impact. • Updated method to be used for PROC MI from section 9.5.1 as per stats team discussion.

Table 1.	Imputation Rules for Incomplete Dates	17
----------	---	----

List of Abbreviations and Definition of Terms

Abbreviation or Term	Definition/Explanation
ACC	American College of Cardiology
AHA	American Heart Association
ANCOVA	analysis of covariance
ApoA1	apolipoprotein A1
ApoB	apolipoprotein B
CI	confidence interval
CRF	case report form
CTCAE	Common Terminology Criteria for Adverse Events
FAS	full analysis set
FCT	fibrous cap thickness
HDL-C	high-density lipoprotein cholesterol
IVUS	intravascular ultrasound
LDL	low-density lipoprotein
LDL-C	low-density lipoprotein cholesterol
Lp(a)	lipoprotein(a)
MI	myocardial infarction
NSTE-ACS	non-ST-segment elevation acute coronary syndrome
OCT	optical coherence tomography
PCSK9	proprotein convertase subtilisin/kexin type 9
QM	monthly (every 4 weeks with a window of \pm 3 days for each visit or dose)
SAT	Safety Assessment Team
SEC	Self-Evident Corrections
SC	subcutaneous
SD	standard deviation
UC	Ultra Centrifugation
VLDL-C	very low-density lipoprotein cholesterol
WHODRUG	World Health Organization Drug

1. Introduction

The purpose of this Statistical Analysis Plan (SAP) is to provide details of the statistical analyses that have been outlined within the protocol for study 20160184, Evolocumab dated 19 April 2018. The scope of this plan includes the final analysis that is planned and will be executed by the Amgen Global Biostatistical Science department unless otherwise specified.

2. Objectives, Endpoints and Hypotheses

2.1 Objectives and Endpoints

Objectives	Endpoints
Primary	

 To evaluate the effect of evolocumab on fibrous cap thickness (FCT) in subjects with non-ST-elevation acute coronary syndrome (NSTEMI-ACS) who are taking maximally tolerated statin therapy. 	
 Absolute change in minimum FCT in a matched segment of artery as determined by optical coherence tomography (OCT) from baseline to week 50.
Secondary	

 To evaluate the effects of evolocumab on coronary plaque morphology in subjects with NSTEMI-ACS who are taking maximally tolerated statin therapy. 	
 Coronary artery segment-based: 
 Percent change in minimum FCT in a matched segment of artery as determined by OCT from baseline to week 50. Absolute change in mean minimum FCT for all images assessed in an individual subject as determined by OCT from baseline to week 50. Absolute change in the maximum lipid arc in a matched segment of artery as determined by OCT from baseline to week 50. Plaque-based: 
 Absolute change in minimum FCT in lipid rich plaques defined as minimum FCT < 120 µm and lipid arc > 90° in at least 3 consecutive images as determined by OCT from baseline to week 50. Absolute change in maximum lipid arc in lipid rich plaques defined as minimum FCT < 120 µm and lipid arc > 90° in at least 3 consecutive images as determined by OCT from baseline to week 50. Absolute change in lipid core length in

Objectives	Endpoints
Secondary(Continued)	
	
 lipid rich plaques defined as minimum FCT < 120 µm and lipid arc > 90° in at least 3 consecutive images as determined by OCT from baseline to week 50.
Safety	

 To evaluate the safety and tolerability of evolocumab treatment in subjects with NSTEMI-ACS who are taking maximally tolerated statin therapy. 	
 Subject incidence of treatment-emergent adverse events and serious adverse events.
Exploratory	

 To evaluate the effects of evolocumab on lipid parameters in subjects with NSTEMI-ACS who are taking maximally tolerated statin therapy To evaluate the effects of evolocumab on features of coronary plaques in subjects with NSTEMI-ACS who are taking maximally tolerated statin therapy using different imaging techniques. 	
 Absolute and percent changes in lipid parameters by visit from baseline. Absolute change in number of microchannels in matched segments of all lesions assessed in an individual subject as determined by OCT from baseline to week 50. Absolute change in macrophage composition in matched segments of all lesions assessed in an individual subject as determined by OCT from baseline to week 50. Absolute changes in lipid content in matched segments of all lesions assessed in an individual subject as determined by IVUS from baseline to week 50.

Page 2 of 2

The primary estimand consists of:

- The target population, which is the adult subjects with NSTEMI-ACS who are taking maximally tolerated statin therapy with or without additional lipid-modifying medication.
- The primary variable, which is the absolute change in minimum FCT in a matched segment of artery as determined by OCT from baseline to week 50.
- The summary measure, which is the mean treatment difference of the primary variable means between evolocumab and placebo.
- The intercurrent events, all randomized subjects who receive at least 1 dose of investigational product regardless of adherence to treatment or commencing commercial proprotein convertase subtilisin/kexin type 9 (PCSK9) inhibitors.

2.2 Hypotheses and/or Estimations

The primary hypothesis is that low-density lipoprotein cholesterol (LDL-C) lowering with evolocumab 420 mg monthly (QM) will result in a greater increase from baseline in

minimum FCT at week 50 than placebo in subjects taking maximally tolerated statin therapy.

3. Study Overview

3.1 Study Design

This is a phase 3, double-blind, placebo-controlled, randomized study evaluating the effect of evolocumab on coronary atherosclerotic plaques as assessed by OCT at baseline and at week 50 in subjects with an NSTEMI-ACS. The trial duration of 1 year was chosen based on the results of several historical trials. Subjects will be randomized 1:1 into 2 treatment groups no more than 7 days after the signing of the informed consent: evolocumab 420 mg subcutaneously (SC) QM or placebo SC QM. The randomization will be stratified by current statin use (> 4 weeks or ≤ 4 weeks duration) at screening. Investigators will up-titrate statin therapy to the maximally tolerated dose, in accordance with local guidelines, for subjects prior to randomization.

3.2 Sample Size

The planned total sample size is 150 subjects (75 randomized to evolocumab 420 mg SC QM and 75 randomized to placebo SC QM). This sample size will provide sufficient power (90%) to determine whether there is a treatment effect of evolocumab relative to placebo in the primary endpoint.

The assumptions in the sample size calculation are based on a linear regression meta-analysis of 7 historical trials ([Dai et al, 2017](#); [Hou et al, 2016](#); [Kataoka et al, 2014](#); [Komukai et al, 2014](#); [Nishio et al, 2014](#); [Hattori et al, 2012](#); [Takarada et al, 2009](#)) weighted by sample sizes.

The analysis result indicates that every 1 mg/dL reduction in LDL-C is estimated to be associated with 1.4785 μm increase in FCT in 12-month follow-up. Assuming a 50 mg/dL reduction in LDL-C, the predicted mean increase (95% CI) in FCT from the meta-analysis was 73.92 (50.97, 96.88) μm. For this study, the assumed treatment effect is at least 50.97 μm increase in FCT, which is approximated from the lower bound 95% CI of the expected change in FCT from the regression model, based on a conservative assumption of 50 mg/dL reduction in LDL-C from baseline to week 50.

The SD of FCT measurement at baseline or at the end of various length of follow-up was reported in a wide range (10.6 to 124 μm) based on 15 to 134 subjects per arm in the historical trials. The SD of change in FCT was only reported in 2 of the 7 trials, ranging from 22 to 86 μm. The assumed common SD for this study is 86 μm to be conservative.

Assuming 1 out of 6 subjects will not complete both baseline and week 50 OCT assessments, and therefore be excluded in the primary analysis, the sample size of 150 subjects will provide approximately 125 subjects in the primary analysis to ensure 90% power to test the study hypothesis.

The sample size calculation was performed using a 2-sided t-test with a 0.05 significance level. The sample size calculation was derived using East® software (version 6.4).

4. Covariates and Subgroups

4.1 Planned Covariates

The following covariates will be used in covariate analyses of the primary endpoint.

Stratification factor:

- current statin use (> 4 weeks or ≤ 4 weeks duration at the time of screening)

Baseline covariates:

- Age
- Sex
- Baseline LDL-C
- Type 2 diabetes mellitus (yes, no)
- Current tobacco use (yes, no)

4.2 Subgroups

Subgroup analysis of the primary endpoint will be conducted for the following subgroups:

Subgroup by stratification factor:

- Current statin use (> 4 weeks or ≤ 4 weeks at the time of screening)

Subgroup by baseline covariates:

- Age (< median, ≥ median; < 65 years of age, ≥ 65 years of age)
- Sex
- Baseline LDL-C (< median, ≥ median)
- Current tobacco use (yes, no)

5. Definitions

5.1 Endpoint Related Definitions

5.1.1 Primary and Secondary Endpoints

Minimum FCT

Minimum FCT in μm for a subject is defined as the minimum of all minimum FCT measurements within each individual frame across all frames of that subject.

Mean Minimum FCT

Mean minimum FCT in μm for a subject is defined as the mean of the minimum FCT measurements performed within all individual frames for that subject.

Maximum Lipid Arc

Maximum Lipid arc in degree for a subject is defined as the maximum of **total** lipid arc measurements within each individual frame across all frames of that subject.

Lipid Core Length

Lipid core length in mm is defined as the longitudinal extent of plaque within the vessel wall that continuously meets the criteria defined in the study protocol. The lipid core length will be **calculated as the number of frames with lipid existence*0.2mm.**

Normalization is also required for lipid core length.

Lipid Rich Plaque

Lipid rich plaque serves as identifier for plaque-based secondary endpoints.

There are three steps to follow to identify frames with lipid rich plaque:

- 1. Identify plaque existence using lipid existence or fibrous existence or calcium existence at baseline. The gap between two independent plaques has to be larger than 5mm (ie, 25 frames)**
- 2. Among plaques detected in step 1 at baseline, verify if they are lipid rich plaque using lipid existence and lipid arc is analyzable and total lipid arc > 90° and FCT existence and FCT < 120 μm in at least 3 consecutive frames**
- 3. Obtain frame numbers for each lipid rich plaque detected in step 1 and 2**

5.1.2 Exploratory Endpoints

Number of Microchannels

Number of microchannels per mm is defined as the sum of microchannels measured from all frames for one subject with a maximal count of 10 per frame. It will be normalized by dividing by the number of frames for each subject **and multiplying by 5.**

Macrophage Composition

Macrophage composition per mm is defined as the sum of macrophage scores from all frames for one subject. It will be normalized by dividing by the number of frames for each subject **and multiplying by 5.**

Lipid Content

For IVUS datasets perform the following across all IVUS frames from both timepoints for a given subject:

- 1. Calculate the plaque area as external elastic membrane cross sectional area (EEM) minus lumen cross sectional area**
- 2. Select frame with maximum plaque area and frame with minimum plaque area in the 10 mm (20 frames) proximal to frame with maximum plaque area**
- 3. Use the EEM value of frame with the maximum plaque area divided by the EEM value of frame with the minimum plaque area to derive remodeling index**
- 4. Use > 1.05 as cut-off to determine if “positive remodeling” is ‘yes’ or ‘no’**
- 5. If “positive remodeling” is ‘yes’ for BL dataset, go to step 6; otherwise this subject data will be excluded for IVUS endpoints**
- 6. Count all frames with plaque area > 63% of EEM and calculate normalized count of frames as $10 \times (\text{the number of frames with plaque area} > 63\% \text{ of EEM}) / (\text{total number of frames})$ at BL and FU, for each subject. Please note the unit would be 'mm/cm artery'.**
- 7. Calculate absolute change in mm/cm artery and percent change of normalized frame count between the two timepoints (BL and FU) as the IVUS endpoints.**

5.2 Study Time Points

Enrollment Date

Enrollment date is defined as the randomization date.

Randomization Date

Randomization Date is defined as the date subject was allocated to a treatment group.

First Dose Date of Investigational Product (First IP Date)

For each subject, the First Dose Date of Investigational Product is defined as the first administration date of the IP as recorded on the IP administration CRF.

Study Day 1

Study Day 1 is defined as the date of first investigational product (IP) administration or the date of randomization for subjects who are not administered any dose of IP.

Study Day

For each subject, and for a given date of interest, study day is defined as the number of days since Study Day 1: Study day = (date of interest – Study Day 1 date) + 1. If the date of interest is prior to the Study Day 1: Study day = (date of interest – Study Day 1 date), so that the day prior to Study Day 1 is study day -1.

Last Dose Date of Investigational Product (Last IP Date)

For each subject, the Last Dose Date of Investigational Product is defined as the date of the last administration of the IP.

Subject-level End of Study (EOS) Date

End of study for each subject is defined as the date the subject last completed a protocol-specified procedure. The date will be recorded on the End of Study CRF page.

Study End Date

The Study End Date is the last EOS date of all randomized subjects.

5.3 Demographics and Baseline Related Definitions

Age

Age is the subject's age in years at enrollment as recorded on the eCRF.

Baseline Lipid and Lipid-related Parameters

Baseline values for LDL-C, triglycerides and troponin are defined as the concentrations measured through **local lab at screening**. **Baseline values for other lipids (eg, total cholesterol, HDL-C and VLDL-C), ApoA1, ApoB, Lp(a) and their derived parameters (eg, ratio between them) are defined as the concentrations measured through central lab on Study Day 1.**

Baseline Laboratory Variables

Baseline values for laboratory variables are defined as the assessment measured at screening.

Baseline Concomitant Medication Usage and Medical History

Baseline values for background statin therapy, lipid-modifying concomitant medication usage and medical history are defined as the assessment measured at screening. For concomitant medication that is not lipid-modifying baseline is defined as measurement at study day 1.

Baseline Image Data

Baseline values for OCT, IVUS image data are defined as the assessment measured at screening.

Baseline Vital Signs

Baseline values for vital signs are defined as the last non-missing value collected prior to or on Study Day 1.

Change (absolute change) from Baseline

The arithmetic difference between a post-baseline value and baseline for a given time point:

Change (absolute change) from baseline = (post-baseline value – baseline value).

Percent Change from Baseline

The percent change from baseline for a given variable at a given time point is defined as:

$100 \times [(value \text{ at given time point} - baseline \text{ value}) / baseline \text{ value}]$.

5.4 Other Study Related Definitions

Actual Treatment Group

A subject's actual treatment group is the randomized treatment group, unless the subject receives treatment throughout the study that is different than the randomized treatment group assignment, in which case the actual treatment group is the treatment received.

Investigational Product (IP)

IP includes AMG 145 SC 420 mg QM and its SC placebo.

IP Exposure Period in Months

For each QM subject: IP Exposure Period = [min (Last IP Date + 28 days, EOS Date) - First IP Date +1] / 365.25 * 12

Study Exposure Period in Months

For each randomized subject, Study Exposure Period = (EOS date – Randomization Date + 1) / 365.25 * 12

Treatment Emergent Adverse Event (TEAE)

Events categorized as Adverse Events (AEs) starting on or after first dose of investigational product as determined by the flag indicating if the adverse event started prior to the first dose of IP on the Events eCRF and up to 30 days after the last dose of IP date or EOS date, whichever is earlier.

Reflexive Approach for LDL-C and VLDL-C

Reflexive approach for LDL-C and VLDL-C is only applicable for the central lab data. When calculated LDL-C is less than 40 mg/dL or triglycerides are > 400 mg/dL, LDL-C and VLDL-C will be measured per ultracentrifugation (UC) instead of calculated LDL-C and calculated VLDL-C, if available.

6. Analysis Sets

6.1 Full Analysis Set

The full analysis set (FAS) includes all randomized subjects who received at least 1 dose of IP. In efficacy analyses, subjects will be grouped according to their randomized treatment group assignment, regardless of the treatment received

6.2 OCT Analysis Set (OAS)

The OCT analysis set includes subjects in the FAS with a baseline **FCT** and an **FCT** measurement conducted on or after week 40.

6.3 Completers Analysis Set (CAS)

The Completers Analysis Set (CAS) includes subjects in the OAS who adhered to the scheduled IP (ie, EOIP reason is completed IP on eCRF) and had an observed value for the primary endpoint.

6.4 Safety Analysis Set

The safety analysis set includes all randomized subjects who have taken at least 1 dose of investigational product. For safety analyses, the subjects will be grouped according to actual treatment group.

7. Planned Analyses

7.1 Interim Analysis and Early Stopping Guidelines

No interim analysis is planned for this study.

7.2 Final Analysis

The final analysis will be conducted after all subjects have either completed all the scheduled study visits or have early terminated from the study. At that time, the database will be cleaned, processed, locked, and a snapshot will be taken; the study will also be unblinded for analyses. Based on the snapshot, efficacy and safety analyses will be performed.

8. Data Screening and Acceptance

8.1 General Principles

The objective of the data screening is to assess the quantity, quality, and statistical characteristics of the data relative to the requirements of the planned analyses.

8.2 Data Handling and Electronic Transfer of Data

The Amgen Global Study Operations-Data Management (GSO-DM) department will provide all data to be used in the planned analyses **including data from RAVE database, imaging data and central lab data (outside of RAVE database). The database will be subjected to edit checks outlined in the Data Management Plan (DMP). Additional details will be provided in DMP and Data Acquisition Requirements Specifications (DARS).**

8.3 Handling of Missing and Incomplete Data

Subjects may be missing specific data points for various reasons. In general, data may be missing due to a subject's early withdrawal from study, a missed visit, or non-evaluability of a data point or endpoint at a time. All attempts will be made to capture missing or partial data for this trial prior to the database lock. The frequency of missing data for efficacy endpoints will be assessed through descriptive summaries of the measurements over time. For subjects with missing post-baseline FCT, the missing primary **and secondary** endpoints will be imputed using multiple imputation.

Adverse event and concomitant medication with completely or partial missing start dates will be queried. After the issue is queried, the date is still incomplete with year only or year and month only, the start date will be imputed as described below:

Table 1. Imputation Rules for Incomplete Dates

	Missing	Imputation	Exception
Start date (AE and concomitant medication)	Day	1	Default to Study Day 1 if an event starts the same year and month as Study Day 1
	Day / Month	1-Jan	Default to Study Day 1 if an event started the same year as Day 1

For historical events (eg, date first taken in the prior statin therapy form) that will be used to summarize data derived stratum, the imputation rules are as follows: if the day is missing, default to 1; if both month and day are missing, default to Jan 1. If the imputed date is on or after the randomization date, default to randomization date minus 1.

Missing years will not be imputed under any condition.

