9.4 Demographic and Baseline Characteristics

All baseline tables will be summarized by randomized treatment group and for all subjects in the FAS. Baseline tables will summarize the following (but not limited to): baseline characteristics, demographics, cardiovascular medical history, and **lipid** parameters. Difference in stratum assignment between randomized stratum and data-derived stratum will be tabulated.

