9.5.1 Analyses of Primary Efficacy Endpoint(s)

Primary Analysis:

To assess the primary endpoint of absolute change in minimum FCT from baseline to week 50, an ANCOVA (Analysis of Covariance) model on the FAS will be used, including terms for treatment group, stratification factor (current statin use [> 4 weeks or ≤ 4 weeks] at screening), baseline minimum FCT as covariates. Least square means and corresponding 95% confidence intervals (CI) will be calculated for each treatment group and for the difference between treatment groups. For subjects with missing post-baseline **minimum FCT**, the **post-baseline minimum FCT value** will be imputed

using multiple imputation. The imputation model will include treatment group, stratification factor, baseline LDL-C, baseline minimum FCT, age as covariates. **At least** five imputations will be conducted, and each complete dataset after imputation will be analyzed using the ANCOVA model. SAS PROC MIANALYZE will be used to combine the results from individual ANCOVA models.

Sensitivity Analysis

- 1) Non-parametric analysis (Quade test) will be performed on FAS as sensitivity analysis. The missing data will be imputed using multiple imputation. **The imputation model and the analysis approach of combining results from multiple imputed datasets will be same as the primary analysis.**
- 2) **COVID-19 Impact sensitivity analysis:**
To determine the impact of COVID-19, a sensitivity analyses will be conducted. All the available post-baseline FCT values will be considered in the analysis, irrespective of the analysis visit window (ie, the post-baseline FCT values after week 56 will also be considered for the analysis). The ANCOVA model for COVID-19 Impact analysis will include the covariates of treatment group, stratification factor (current statin use [> 4 weeks or ≤ 4 weeks] at screening), baseline minimum FCT as covariates. The imputation method, model and analysis approach will be same as the primary analysis.

Covariate and Subgroup Analysis

In addition to the primary analysis, covariate adjusted analysis of the primary efficacy endpoint will be performed as supportive analyses using the baseline covariates in [Section 4.1](#), in their original format, one at a time, in the ANCOVA model used in the primary analysis.

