Subgroup analyses on the primary efficacy endpoint will be conducted using the subgroups specified in [Section 4.2](#), in the ANCOVA model used in the primary analysis. Subgroup by treatment interactions will be tested and the p-value of the interaction term will be reported.

For covariate and subgroup analyses, the data-derived stratification factor from the CRF will be used.

Supplementary Analysis:

The following additional analyses will also be performed to evaluate the robustness of the primary analysis result:

- The primary analysis will be repeated using OAS
- The primary analysis will be repeated using CAS

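### The partial-date rule behind the CRF-derived statin stratum can err only towards > 4 weeks, and a missing start year has no fallback

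*SAP*

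**What the plan says.** The stratification factor is set out in SAP 3.1: "The randomization will be stratified by current statin use (> 4 weeks or ≤ 4 weeks duration) at screening". SAP 4.2 lists the same split as a subgroup for the primary endpoint, and SAP 9.5.1 reports an interaction p-value for each subgroup.

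For the supportive models SAP 9.5.1 names the source of the factor: "For covariate and subgroup analyses, the data-derived stratification factor from the CRF will be used".

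SAP 8.3 has a separate rule for historical dates. It gives the first-taken date on the prior statin form as its example and links the rule to the derived stratum: "if the day is missing, default to 1; if both month and day are missing, default to Jan 1". If the result falls on or after randomisation, it is reset to the day before randomisation. Then: "Missing years will not be imputed under any condition". No stratum is specified for a subject whose date remains unusable.

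SAP 9.4 adds a check: "Difference in stratum assignment between randomized stratum and data-derived stratum will be tabulated". It does not say how discordant or missing cases are handled.

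**The concern.** The default is the earliest date that the recorded part allows. That is harmless for a long-term user, but the stratum turns on 28 days, the same order as the gap the default can open. A start on 20 March recorded only as March, with screening on 5 April, is 16 days of use in truth and 35 days as imputed. The subject moves from the ≤ 4-week to the > 4-week group.

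Three things are at stake, all outside the confirmatory testing:

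- The > 4-week subgroup can take in recent starters while the ≤ 4-week subgroup takes in no long-term users, so the contrast between them is pulled towards zero.
- A subject with no start year has no derived stratum under the rule as written. Unless some unwritten step supplies one, that subject cannot enter a model containing the term. Such subjects are plausibly long-term users, so the loss would be selective.
- The SAP 9.4 table would mix disagreements created by the date rule with real differences between what was entered at randomisation and what the CRF shows.

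**Working it through.** The plan gives no figure for stratum misclassification, so there is none to reproduce. Its sample size, used only for scale in step 4, does reproduce: a two-sided t-test with difference 50.97 µm, SD 86 µm, alpha 0.05 and 90% power needs 61 per arm, or 122 evaluable and 147 randomised, against the stated 125 and 150.

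**Inputs.** From the documents: the 4-week cut at screening (SAP 3.1), the date rule and its reset (SAP 8.3), and 150 subjects, 125 evaluable, SD 86 µm (SAP 3.2). Assumed: 4 weeks = 28 days; true starts uniform over 0 to 28 days before screening (29 possible lags); screening dates spread evenly over the calendar.

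**1. Day missing.** Let D be the day of the month at screening.
- For D = 1 to 28, the subject is moved when the start lies in the previous month, which holds for 29 − D of the 29 lags. Summed over D, 406/29 = 14 days per month, or 168 of 365.25 days = 46.0%.
- For D = 30 or 31, the first of the same month is already more than 28 days back, so every lag is moved: 18/365.25 = 4.9%.
- Exception: for screening on 1 March in a non-leap year, 1 February is exactly 28 days back: 0.75 × (28/29)/365.25 = 0.2%.
- Total: 46.0 + 4.9 − 0.2 = **50.7%**.

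**2. Day and month missing.** The stratum survives only if screening falls on 1 to 29 January and the start is in the same year. That is D of the 29 lags for each D: 435/29 = 15 days, and 15/365.25 = 4.1%. Moved: **95.9%**.

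Enumerating every screening date from 2017 to 2020 gives the same two figures. The reset to the day before randomisation fires in at most 0.4% of cases. No true > 4-week user moves the other way. For starts only 0 to 7 days before screening, the figures are 16.3% and 93.0%.

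**3. Effect on the subgroup contrast.** Let q be the true ≤ 4-week share, p the share of that group with a partial date, and f the moved fraction from step 1 or 2. Then moved = 150 × q × p × f, and the contrast is multiplied by 1 − moved / (150 × (1 − q) + moved). Neither q nor p is in the documents. With p = 10%:

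| q | Day missing: moved | Contrast × | Day and month missing: moved | Contrast × |
|---|---|---|---|---|
| 0.2 | 1.5 of 30 | 0.987 | 2.9 of 30 | 0.977 |
| 0.5 | 3.8 of 75 | 0.952 | 7.2 of 75 | 0.913 |
| 0.8 | 6.1 of 120 | 0.831 | 11.5 of 120 | 0.723 |

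At q = 0.5, letting p run from 5% to 30% moves about 2 to 11 subjects (day missing; factor 0.975 to 0.868) or 4 to 22 (day and month missing; 0.954 to 0.777).

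**4. Scale.** With 125 subjects in four equal cells, the interaction standard error is 4 × 86/√125 = 30.8 µm. If the true interaction were as large as the assumed treatment effect, a 5% shrinkage would be 0.05 × 50.97 = 2.5 µm, or about 0.08 standard errors.

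**The case against.** The strongest reply is that the numbers will be small and the analyses do not decide the trial. Most of that stands.

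- Eligibility (Protocol 6.1) admits subjects on no statin. If they count as ≤ 4 weeks, they have no prior start date to impute. Some recent starters will have begun in hospital with an exact date on record. Partial dates probably cluster in long-term users, for whom the default does no harm. The rates in steps 1 and 2 therefore apply only to recent starters with incomplete dates, not to the whole ≤ 4-week group.
- SAP 8.3 commits to chasing missing and partial data before lock, and the SAP 9.4 table would bring disagreements to light. Both reduce the problem, but neither says what to do with a date that stays incomplete.

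Three stronger readings are tempting, and the documents do not support them.

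- A reader might infer that replacing the randomised stratum with a derived one is itself a mistake. It is a prespecified choice with a real merit: it corrects entries mis-keyed at randomisation.
- A reader might infer that the covariate models, described as adding terms "one at a time, in the ANCOVA model used in the primary analysis", also swap the stratum variable, so that a shift from the primary result could not be attributed to the covariate. That requires the primary model to use the randomised stratum. SAP 9.5.1 describes its factor only as "stratification factor (current statin use [> 4 weeks or ≤ 4 weeks] at screening", and Protocol 10.3.2.2 says at randomisation. Neither names the source.
- A reader might infer that subjects with no start year are certain to be dropped. The SAP is silent, and the first-taken date is given as an example of the inputs. What can be said is that no fallback is written.

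**Conclusion.** The point holds as a minor one. The date rule suits its purpose poorly: against a 4-week cut, the earliest-date default can misclassify in one direction only. It moves about half of true recent starters with the day missing and about 96% with day and month missing, if starts are uniform over the 4 weeks before screening. A start with no year yields no derived stratum under the written rule.

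The reach is limited to subjects with incomplete start dates, in the covariate and subgroup analyses. The sentence that brings in the CRF-derived factor does not extend to the primary analysis, and the sample size and the Hochberg procedure are untouched. How many subjects are affected depends on the partial-date rate and the stratum split, which are not given. In the central illustration (half at ≤ 4 weeks, 10% of them lacking the day) the subgroup contrast loses about 5%, far below its sampling error. The case for acting is that a better rule costs almost nothing.

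**What to change.** In SAP 8.3, derive the stratum from a partial start date only when every date consistent with the recorded part gives the same stratum. In all other cases, including a missing year, use the randomised (IVRS/IWRS) stratum. Because randomisation was stratified on this factor, that value should exist for every randomised subject.

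With screening on 5 April:
- A record of February only is decided: its latest possible start is 36 days back, so > 4 weeks.
- A record of 2015 only is likewise decided as > 4 weeks.
- A record of March only allows anything from 5 to 35 days, so the randomised stratum is used.

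This is better than deleting the default outright, which would discard dates that settle the stratum without ambiguity.

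In the SAP 9.4 table, flag the fallback subjects separately so that a copied randomised value is not counted as agreement.

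The cost is a few sentences in the SAP and no new data. One small downside remains: a subject mis-keyed at randomisation whose start date is also ambiguous keeps the mis-keyed stratum.
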